9. STATISTICAL CONSIDERATIONS

9.1. Statistical Hypotheses

9.1.1. Primary Hypothesis

The primary hypothesis for this study is that ravulizumab is superior to placebo in decreasing proteinuria. Hypothesis testing will be one-sided and performed at the 0.05 level of significance.

9.2. Sample Size Determination

This study plans to enroll 60 participants in both the IgAN and LN cohorts in a 2:1 ratio to ravulizumab and placebo, for a total of 120 participants.

In March 2018, a National Kidney Foundation (NKF)-sponsored workshop on surrogate endpoints for clinical studies in early stages of CKD proposed that a 20% to 30% reduction in the geometric mean of proteinuria was likely to be necessary to ensure a significant treatment effect on the clinical outcome (Levey, 2020; Holtkamp, 2020).

Individual patient data from relevant studies in IgAN was previously used to estimate variability and expected changes in proteinuria for patients treated with placebo in addition to allowed concomitant standard of care treatment (Fellstrom, 2017). Based on this data, the geometric mean ratio (GMR) of 26-week to baseline proteinuria values is assumed to be 0.85 (ie, a 15% reduction in proteinuria) for the placebo group. In order to target at least a 30% relative treatment effect, the GMR is assumed to be 0.55 (ie, a 45% reduction in proteinuria) for the ravulizumab group.

Expected changes in proteinuria and associated variability were not available on the log-scale for patients with LN; however, 2 studies of patients with LN who were treated with MMF showed mean proteinuria values of approximately 4.0 g/day at baseline and approximately 2.0 g/day at Week 24 (Appel, 2009; Ginzler, 2005). The GMR of 26-week to baseline proteinuria values is assumed to be 0.60 (ie, a 40% reduction in proteinuria) for the placebo group. In order to target at least a 30% relative treatment effect, the GMR is assumed to be 0.40 (ie, a 60% reduction in proteinuria) for the ravulizumab group.

Sample size calculations are based on a one-sided two-sample t-test of log-transformed proteinuria values. The log change from baseline in proteinuria is calculated as $\log(0.85)$ and $\log(0.55)$ for the placebo and ravulizumab treatment groups, respectively, for the IgAN cohort, and as $\log(0.60)$ and $\log(0.40)$ for the placebo and ravulizumab treatment groups, respectively, for the LN cohort. A common standard deviation (SD) of log change is assumed to be 0.60 (Fellstrom, 2017). Under these assumptions and an anticipated 10% drop out rate, a sample size of 60 participants (40 participants randomized to ravulizumab, 20 participants randomized to placebo) will provide approximately 80% power to detect a treatment difference with a one-sided significance level of 0.05 in each cohort.

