9.4.1. Efficacy Analyses

9.4.1.1. Analyses of Primary Efficacy Endpoint

The primary analysis of the primary efficacy endpoint will be based on the Full Analysis Set (FAS).

For the LN cohort, proteinuria will be measured by UPCR in g/g derived from a single 24-hour urine collection at Screening and the mean of 2 separate 24-hour urine collections at Week 26.

For the IgAN cohort, proteinuria will be measured by absolute protein in g/day derived from the mean of 2 valid 24-hour urine collections.

To reduce skewness, the natural logarithm will be used to transform proteinuria values before analysis. An analysis of covariance (ANCOVA) will be used for the primary efficacy endpoint to compare reductions in proteinuria between the ravulizumab and placebo treatment groups. The ANCOVA model will include change from baseline in log-transformed proteinuria as the response variable and will adjust for baseline log proteinuria and the randomization stratification factor. The treatment effect will be evaluated using the least squares mean difference between treatment groups. The point estimate and two-sided 90% confidence interval (CI) for the mean difference of log-transformed proteinuria will be back-transformed (via exponentiation) to obtain the GMR and corresponding two-sided 90% CI. The values will then be expressed as percentage change in adjusted geometric mean of proteinuria at Week 26 relative to baseline.

For the LN cohort, data collected on or after receipt of additional standard of care therapy will be imputed using the proteinuria value from the 24-hour urine collection performed at the time of Renal Flare for the primary efficacy analysis. Additional sensitivity analyses will be performed to assess the impact of the missing data and assumptions.

For the IgAN cohort, participants initially randomized to the placebo group will receive ravulizumab in the Extension Period. Therefore, analysis of the secondary endpoints during the Extension Period will be summarized separately for each treatment group and baseline for the placebo group will be re-defined as the last measurement taken before the first dose of ravulizumab during the Extension Period (ie, the Week 26 measurement).

The primary efficacy endpoint analysis will also be performed on the Per Protocol Set.

Full details of these analyses will be provided in the SAP.

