Sample size calculations are based on a 1-sided, 2-sample t-test of log-transformed proteinuria values. The log change from baseline in proteinuria is calculated as $\log(0.85)$ and $\log(0.55)$ for the placebo and ravulizumab treatment groups, respectively, for the IgAN cohort and as $\log(0.60)$ and $\log(0.40)$ for the placebo and ravulizumab treatment groups, respectively, for the LN cohort. A common standard deviation (SD) of log change is assumed to be 0.60 ([Fellstrom, 2017](#)). Under these assumptions and an anticipated 10% drop out rate, a sample size of 60 participants (40 participants randomized to ravulizumab, 20 participants randomized to placebo) will provide approximately 80% power to detect a treatment difference with a 1-sided significance level of 0.05 in each cohort.

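### The plan's own sizing inputs give about 80% power for IgAN but only about 75% for LN, so the single figure claimed for each cohort is wrong for LN

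*Protocol*

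**What the plan says.** Protocol section 9.2 sizes both cohorts with one method: "Sample size calculations are based on a one-sided two-sample t-test of log-transformed proteinuria values". The level comes from section 9.1.1: "Hypothesis testing will be one-sided and performed at the 0.05 level of significance". Most inputs are shared. On variability, "A common standard deviation (SD) of log change is assumed to be 0.60". On numbers, "Under these assumptions and an anticipated 10% drop out rate, a sample size of 60 participants" (40 ravulizumab, 20 placebo) is said to be enough.

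Only the assumed effects differ. For IgAN the ratio of Week 26 to baseline proteinuria is 0.85 on placebo and 0.55 on ravulizumab. For LN it is 0.60 on placebo and 0.40 on ravulizumab.

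From this the protocol concludes that the design "will provide approximately 80% power to detect a treatment difference with a one-sided significance level of 0.05 in each cohort". SAP section 3 repeats the inputs and the conclusion: it "will provide approximately 80% power to detect a treatment difference with a 1-sided significance level of 0.05 in each cohort".

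The primary analysis itself is not a t-test. Protocol section 9.4.1.1 and SAP section 5.3.2 specify an ANCOVA on the change in log proteinuria that "will adjust for baseline log proteinuria and the randomization stratification factor".

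**The concern.** With the same sample size, SD, alpha and dropout in both cohorts, power depends only on the log difference between arms. That difference is smaller in LN than in IgAN, so the two powers cannot be equal. The question is whether the gap is small enough for one rounded figure to cover both.

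If it is not, the plan understates the chance of missing an LN effect of the size it assumes. That affects how a non-significant LN result at Week 26 would be read, and protocol section 9.5.2 says that analysis will inform Phase 3 planning.

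**Working it through.** **Inputs (Protocol section 9.2, repeated in SAP section 3)**

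- One-sided alpha 0.05, two-sample t-test on the log change
- SD of log change 0.60 in both arms and both cohorts
- 40:20 randomised, 10% dropout. Applied equally to both arms this leaves 40 × 0.9 = 36 and 20 × 0.9 = 18. The documents do not print 36:18; it is the natural reading of the dropout rate.
- Log differences: IgAN ln(0.85/0.55) = 0.4353; LN ln(0.60/0.40) = 0.4055

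**Formula**

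SE = SD × √(1/n₁ + 1/n₂); noncentrality = log difference / SE; degrees of freedom = n₁ + n₂ − 2. Power is the probability that a noncentral t exceeds the one-sided 5% critical value.

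At 36:18, SE = 0.60 × √(1/36 + 1/18) = 0.1732, with 52 degrees of freedom.

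**Step 1: reproduce the plan's figure (IgAN).** Noncentrality = 0.4353 / 0.1732 = 2.513. Power = **79.8%**. This matches the claim, which supports 36:18 as the intended basis.

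**Step 2: the same calculation for LN.** Noncentrality = 0.4055 / 0.1732 = 2.341. Power = **74.7%**. A simulation of 200,000 trials at 36:18 also gave 74.7%.

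**Step 3: can another convention give about 80% in LN?**

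| Basis | IgAN | LN |
|---|---|---|
| t-test, 36:18 | 79.8% | 74.7% |
| Normal approximation, 36:18 | 80.7% | 75.7% |
| t-test, 40:20 (no dropout) | 83.5% | 78.6% |
| t-test, 34:20 (all six dropouts on ravulizumab) | – | 76.5% |
| t-test, 37:17 (three dropouts in each arm) | – | 73.6% |

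The gap is not a t-versus-normal rounding effect. LN approaches 80% only with no dropout, which contradicts the sentence and moves IgAN to 83.5%.

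**Step 4: what LN would need for 80%.** With the same inputs, 63 evaluable (42:21) give 80.4%. That is 63 / 0.9 = 70 randomised, against 60 planned. At 36:18, the SD would have to be about 0.557 and not 0.60.

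**Step 5: the planned ANCOVA.** Suppose the covariates have correlation R with the log change. The documents give no value, so R is an assumption. The residual SD is 0.60 × √(1 − R²), with 50 degrees of freedom. LN power at 36:18:

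| R | LN power |
|---|---|
| 0 (unadjusted t-test) | 74.7% |
| 0.2 | 76.2% |
| 0.3 | 78.1% |
| 0.4 | 80.9% |

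LN reaches 80% at R of about 0.37 (R² about 0.14).

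**The case against.** The strongest reply is that the t-test is not the primary analysis. Change from baseline contains the baseline value with a negative sign, so some correlation between the two is expected. If log proteinuria has equal variance at both times, R = √((1 − ρ)/2), where ρ is the correlation between baseline and Week 26. R of 0.37 then needs only ρ of about 0.725 or less. LN power would be 82.6% at ρ = 0.6, 80.5% at 0.7, 78.5% at 0.8 and 77.5% at 0.85. The LN baseline is a single 24-hour collection, and its measurement noise would tend to lower ρ. So the primary analysis may well have power near 80%.

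That stands as a statement about the trial's likely operating power. It does not rescue the sentence, which attributes its figure to an unadjusted t-test and states no correlation. Adjustment would also raise IgAN if its covariates are predictive, so it does not explain one figure for both cohorts.

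A second reply is that "approximately" is loose and the inputs are soft. Section 9.2 says log-scale variability was not available for LN, and the 0.60 cites the same source as the IgAN data. LN power at 36:18 is 80.9% at an SD of 0.55 and 68.7% at 0.65. It is true that a change of 0.05 in a borrowed SD matters as much as the whole gap. But the uncertainty runs in both directions, and a stated power should still follow from the stated inputs.

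Finally, this is a Phase 2 proof-of-concept study whose Week 26 analysis does not alter its progression. No estimate, confidence interval or p-value changes. That limits the severity; it does not make the figure right.

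**Conclusion.** The concern holds. For the sizing test the plan describes, LN power is 74.7% (75.7% by normal approximation), about 5 points below the stated figure, while IgAN reproduces at 79.8%. The result rests on the plan's SD of 0.60, its assumed ratios, and 10% dropout applied equally to both arms. Of the alternative dropout readings tried, none gives about 80% in LN while keeping the stated dropout.

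This is a should-fix matter of one misstated figure. The validity of the test, the alpha and the estimand are unaffected. The power of the ANCOVA cannot be determined from the documents.

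**What to change.** In Protocol section 9.2 and SAP section 3, replace the single power figure with one per cohort: approximately 80% for IgAN and approximately 75% for LN. Describe both as the power of the unadjusted one-sided two-sample t-test after 10% dropout, and give the evaluable numbers (36:18).

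If the sponsor relies on covariate adjustment to reach 80% in LN, state the assumed correlation between the covariates and the log change (about 0.37 is needed) and its source.

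The cost is one sentence in each document and a less favourable LN figure. Sample size, test, alpha and estimand stay as they are.

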9.3. Populations for Analyses

The following populations are defined for this study:

Population	Description
Randomized Set	All randomized participants. Participants will be analyzed as randomized for reporting disposition, demographics, and baseline characteristics.
Full Analysis Set (FAS)	All randomized participants who receive at least 1 dose of study drug. Participants will be analyzed as randomized for reporting efficacy data.
Modified Full Analysis Set (mFAS)	The mFAS is a subset of the FAS, excluding participants who were impacted by COVID-19.
Safety Set	All participants who receive at least 1 dose of study drug. Participants will be analyzed according to the study drug they actually received for reporting exposure and safety data.
Per Protocol Set	All randomized participants who receive at least 1 dose of study drug and without important protocol deviations.
Pharmacokinetic (PK) Analysis Set	All participants who receive at least 1 dose of study drug and who have evaluable PK data.
Pharmacodynamic (PD) Analysis Set	All participants who receive at least 1 dose of study drug and who have evaluable PD data.

Abbreviations: PD = pharmacodynamic; PK = pharmacokinetics

9.4. Statistical Analyses

Statistical methods described in this section will be further elaborated in a separate Statistical Analysis Plan (SAP). All efficacy and safety analyses will be summarized separately for the Initial Evaluation Period, Extension Period, and Post-treatment Follow-up Period. Limited data will be collected during the Post-treatment Follow-up Period and will be summarized descriptively as applicable.

Summary statistics will be computed and displayed by treatment group and by visit, where applicable. Descriptive statistics for continuous variables will minimally include the number of participants, mean, SD, minimum, median, and maximum. For categorical variables, frequencies, and percentages will be presented. Graphical displays will be provided as appropriate.

Analyses will be performed using the SAS® software Version 9.4 or higher.

The analyses for participants in the LN cohort and participants with IgAN cohort will be conducted and reported separately. Participants in each disease-specific cohort will be analyzed as randomized, regardless of actual treatment received.

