	Absolute values and change from baseline in ravulizumab concentrations over time
To characterize the potential for immunogenicity of ravulizumab in adult participants with LN or IgAN	Incidence of ADAs over time
Safety (Both Cohorts)	
To characterize the safety and tolerability of ravulizumab in adult participants with LN or IgAN	Incidence of AEs and SAEs over time

Abbreviations: ADA = antidrug antibody; AE = adverse event; C3, C4, and C5 = complement components 3,4, and 5; CRR = complete renal response; eGFR = estimated glomerular filtration rate; IgAN = immunoglobulin A nephropathy; LN = lupus nephritis; PD = pharmacodynamics; PK = pharmacokinetics; PRR = partial renal response; SAE = serious adverse event; SLE = systemic lupus erythematosus; UPCR = urine protein to creatinine ratio

Overall Design

Study ALXN1210-NEPH-202 is a Phase 2, randomized, double-blind, placebo-controlled, multicenter study of ravulizumab in addition to allowed concomitant therapy consistent with the standard of care in 120 adult participants (18 to 75 years of age) with either LN or IgAN. All participants must be naive to complement inhibitor treatment and have either a diagnosis of LN with an active flare or IgAN based on kidney biopsy, estimated glomerular filtration rate (eGFR) \geq 30 mL/min/1.73m², and proteinuria [defined as urine protein to creatinine ratio (UPCR) \geq 1 g/g from one 24-hr urine collection (LN cohort) or as mean protein \geq 1 g/24-hr from 2 valid 24-hr collections (IgAN cohort)]. Participants in the IgAN cohort must have been treated with stable doses of the maximum tolerated renin-angiotensin system (RAS)-inhibiting medications and have controlled, stable blood pressure (< 140/90 mmHg) for \geq 3 months prior to Screening.

Approximately 60 participants in each disease cohort will be randomly assigned in a 2:1 ratio to receive ravulizumab or placebo (40 ravulizumab, 20 placebo). Randomization will be stratified by whether corticosteroid induction treatment was initiated prior to Screening versus during the Screening Period for participants in the LN cohort and by mean proteinuria (1 to 2 g/day versus $>$ 2 g/day) from 2 valid 24-hr urine collections during Screening Period for participants in the IgAN cohort.

The study consists of an up to 6-week Screening Period, a 26-week Initial Evaluation Period, a 24-week Extension Period, and a 36-week post-treatment Follow-up Period.

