During the Initial Evaluation Period, all participants will receive a weight-based loading dose of ravulizumab or placebo on Day 1, followed by maintenance doses of ravulizumab or placebo on Day 15 and then once every 8 weeks (q8w) thereafter. Loading and maintenance doses will be determined based on body weight (see table below). All participants will receive allowed

concomitant therapy consistent with the standard of care for participants with LN and IgAN throughout the study.

During the 24-week Extension Period, participants in the LN cohort will continue to receive their randomized allocation of study drug (ravulizumab or placebo) q8w. Participants in the LN cohort will receive additional standard of care therapy in the event of a protocol-defined Renal Flare or Severe Extrarenal systemic lupus erythematosus (SLE) Flare. Approved novel treatment(s) for LN is allowed. Additional standard of care therapy for participants with Suboptimal Response is allowed at the clinical discretion of the Investigator in conversation with the Medical Monitor. For the IgAN cohort, participants in the placebo group will receive a blinded loading dose of ravulizumab at Week 26 and participants in the ravulizumab group will receive a blinded ravulizumab dose of 900 mg at Week 26. Starting Week 28, all participants in the IgAN cohort will receive open-label weight-based doses of ravulizumab q8w until the end of the Extension Period.

During the 36-week Post-treatment Follow-up Period, all participants will continue to receive standard of care and will be monitored for safety, clinical events of interest, and kidney function. Participants who discontinue study drug early and agree to remain in the study should continue to attend their scheduled protocol visits until Week 50. During these visits, all assessments except for study drug administration should be performed according to the Schedule of Assessments. Participants who withdraw from the study will be followed for safety until 8 weeks after the last dose of study drug. The end of study is defined as the last participant's last visit in the Post-treatment Follow-up Period.

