Serious infection	
Apart from the predictable risk of infection with Neisseria species, which is well known and directly related to the mechanism of action of ravulizumab, the mechanism that may lead to other serious infections in participants treated with ravulizumab remains unclear. Since the relevance of serious infection with ravulizumab therapy has not been confirmed in clinical studies, this remains a potential risk. In this study, because participants with LN will be immunosuppressed due to concomitant steroid and MMF use, they will be at increased risk of serious infections due to the immunosuppressant use.
	
All participants will be required to be vaccinated for Hib and S pneumonia, according to current national/local guidelines, in addition to N meningitidis. Healthcare professionals and participants should have increased awareness about the potential risk of serious infection. Monitoring for signs and symptoms of serious infections will be conducted as part of the safety assessments for this study.

Immunogenicity	
Treatment with any therapeutic protein has the potential to induce an immune response. Potential clinical consequences may include hypersensitivity, anaphylaxis or related type of reactions or loss of efficacy.
 
Fewer than 1% of participants in the ravulizumab Phase 2 and 3 studies had positive ADA samples.
	
Monitoring for hypersensitivity and serious infusion-related reactions will be conducted as part of safety assessments for this study (Section 10.4).
 
Infusion should be stopped in the event of any intervention-related severe adverse events like systemic hypersensitivity or anaphylaxis.
 
In case of suspected SAEs of hypersensitivity or anaphylaxis, additional ADA samples may be collected during or in proximity of the event.

Pregnancy exposure/lactation	
No studies of ravulizumab have been conducted in pregnant or breastfeeding women. There are no data available on excretion of ravulizumab in breast milk.
	
Pregnant or nursing female participants will be excluded from the clinical study. Women and men enrolled in the study, and their spouses/partners, must use a highly effective or acceptable method of contraception for a period of 8 months following the final dose of study intervention. Breastfeeding should be discontinued during treatment and up to 8 months after treatment with ravulizumab (Section 10.6).

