6.3.2. Blinding

Participants, all investigative site personnel, and any Alexion employee, or designee, directly associated with the conduct of the study will be blinded to participant treatment assignments during the Initial Evaluation Period. The blinding will be maintained by using identical study drug kits and labels for ravulizumab and placebo. The placebo will have an identical appearance to that of ravulizumab. The randomization code will be maintained by the IRT provider.

The primary endpoint evaluation will occur for each disease-specific cohort after all participants in the disease-specific cohort complete the Week 26 Visit or withdrawn from the study prior to Week 26. Alexion will be unblinded at this time to conduct the primary analysis.

After completion of the Initial Evaluation Period, participants in the LN cohort will continue receiving their randomized study drug and both the participants and the investigative site personnel will remain blinded for the remaining 24-week Extension Period. For the IgAN cohort, participants in the placebo group will switch to receive a blinded loading dose of ravulizumab after completion of the protocol-required assessments at the Week 26 Visit and participants in the ravulizumab group will receive a blinded ravulizumab dose of 900 mg at Week 26. The 900 mg dose at Week 26 was chosen to ensure maintenance of complete C5 inhibition until the next scheduled maintenance dose. Following completion of the Week 26 Visit, participants in the IgAN cohort will receive open-label ravulizumab treatment during the 24-week Extension Period.

In case of an emergency, the Investigator has the sole responsibility for determining if unblinding of a patient's intervention assignment is warranted. Patient safety must always be the first consideration in making such a determination. If the Investigator decides that unblinding is warranted, the Investigator will be able to unblind the patient's treatment allocation directly using the IRT. If a patient's intervention assignment is unblinded, the Sponsor must be notified within 24 hours after breaking the blind. The date and reason that the blind was broken must be recorded in the source documentation, as applicable.

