5.1.2. Data Presentation for the Extension Period

Data summaries for the Extension Period will be presented by randomized treatment group and overall, if applicable. For the IgAN cohort, summaries will be presented by treatment sequence (ie, “Ravulizumab to Ravulizumab” and “Placebo to Ravulizumab”). In addition, baseline for the IgAN cohort will be defined as the last value prior to their initial exposure to ravulizumab.

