5.6. Safety Analyses

All safety analyses will be performed on the Safety Set and will be based on the actual treatment received. All safety data will be provided in patient listings by treatment group.

AEs will be coded in MedDRA V 23.0 or higher and presented by MedDRA system organ class (SOC) and preferred term (PT).

No formal hypothesis is planned. Safety data will be presented separately for the Initial Evaluation Period, Extension Period, and Post-treatment Follow-up Period.

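### LN cohort: safety is tabulated by arm only within periods split at Week 26, and no cumulative Day 1 to Week 50 adverse event incidence by arm is specified, although randomized treatment continues to Week 50

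*Protocol*

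**What the plan says.** Protocol 9.4 sets one layout rule for both cohorts: "All efficacy and safety analyses will be summarized separately for the Initial Evaluation Period, Extension Period, and Post-treatment Follow-up Period". SAP 5.1 repeats it, and SAP 5.6 applies it to safety: "Safety data will be presented separately for the Initial Evaluation Period, Extension Period, and Post-treatment Follow-up Period". Under SAP 5.1.1 the Week 26 dose opens the Extension Period.

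The LN cohort does not change treatment at that dose. The Protocol synopsis says that "participants in the LN cohort will continue to receive their randomized allocation of study drug (ravulizumab or placebo) q8w" during the Extension Period. Protocol 6.3.2 adds that "both the participants and the investigative site personnel will remain blinded for the remaining 24-week Extension Period". The sponsor is in a different position once the cohort reaches its Week 26 analysis: "Alexion will be unblinded at this time to conduct the primary analysis". In IgAN, by contrast, placebo participants receive a ravulizumab loading dose at Week 26.

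Weeks 26 to 50 are still displayed by arm. SAP 5.1.2 says: "Data summaries for the Extension Period will be presented by randomized treatment group and overall, if applicable".

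SAP 5.6.2 counts an event as treatment-emergent from the first infusion to 56 days after the last. It counts each participant once per category and bases percentages on treated Safety Set participants in the arm. SAP 5.6 plans no formal safety hypothesis. SAP 5.8.5 says the Week 50 analysis contains all planned safety analyses, which are the period-specific ones.

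**The concern.** A split designed around the IgAN crossover is applied to a cohort that has no crossover. LN has 50 weeks of randomized, site-blinded exposure. The natural safety summary is the proportion of participants in each arm with a given event over that time, and neither document asks for it.

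The stated safety endpoint is the incidence of AEs and SAEs over time. LN efficacy events (renal flare, extrarenal flare, treatment failure, suboptimal response) are already summarized cumulatively through Week 50 in SAP 5.4.8 to 5.4.11. Adverse events in the same participants are not. Table 6 in Protocol 2.3.1 says of LN participants that "they will be at increased risk of serious infections due to the immunosuppressant use", and the Protocol synopsis states that there is no data monitoring committee. At stake is how clearly a reader of the report can see a difference between arms that builds up over the whole treatment period.

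**Working it through.** **No plan figure to reproduce.** Neither document gives a safety event rate, a safety test or a safety power.

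**Period lengths.** The Protocol synopsis gives "a 26-week Initial Evaluation Period, a 24-week Extension Period". That is 26 + 24 = 50 weeks, so 24/50 = 48% of LN randomized time falls in the Extension tables.

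**TEAE window.** The last scheduled LN dose is Week 42, Day 295 (Protocol Table 3). 295 + 56 = Day 351, which is the Week 50 visit. For a participant who completes treatment, the TEAE window therefore coincides with the randomized period. Only the display is divided.

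**Why the two tables do not add up.** Let A be the participants with the event in Weeks 0 to 26 and B those with it in Weeks 26 to 50. Cumulative incidence needs A + B minus those in both. The period tables give A and B, not the overlap. Event counts can be summed across the tables, but participant counts cannot.

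**Illustration of size.** The assumptions below are not in the documents, except the arm sizes (40 ravulizumab, 20 placebo):
- constant hazard and no dropout;
- all treated participants as the denominator in both periods;
- the two periods independent;
- a one-sided Fisher exact test at 0.05 as the yardstick for a visible difference.

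Risk over t weeks = 1 − (1 − p26)^(t/26). For p26 = 20% versus 5%:
- 24 weeks: 1 − 0.80^(24/26) = 18.6% and 1 − 0.95^(24/26) = 4.6%
- 50 weeks: 1 − 0.80^(50/26) = 34.9% and 1 − 0.95^(50/26) = 9.4%

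Exact enumeration at 40 versus 20 gives 0.321 for Weeks 0 to 26, 0.290 for Weeks 26 to 50 and 0.607 pooled. The chance that at least one period table flags is 1 − (1 − 0.321)(1 − 0.290) = 0.52.

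| 26-week risks | Weeks 0–26 | Weeks 26–50 | Either table | Pooled 0–50 | Pooled minus either |
|---|---|---|---|---|---|
| 20% vs 5% | 32% | 29% | 52% | 61% | 9 points |
| 25% vs 5% | 50% | 47% | 73% | 82% | 8 points |
| 30% vs 10% | 41% | 38% | 64% | 69% | 6 points |
| 15% vs 5% | 15% | 13% | 26% | 34% | 7 points |

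The pooled table gains 18 to 32 points over the Week 26 table alone. Against both planned tables read together, it gains about 5 to 9. Reading two tables also gives two chances of a false flag, so the last column slightly understates the advantage of pooling.

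**Sensitivity.**
- These scenarios imply large hazard ratios, ln(1 − p1)/ln(1 − p0), from ln(0.85)/ln(0.95) = 3.2 to ln(0.75)/ln(0.95) = 5.6.
- For 10% versus 5% at 26 weeks, the same test flags 4% from the Week 26 table and 12% pooled.
- With a two-sided test, 50-week placebo risks of 5% to 30% and hazard ratios of 2 or 3, pooled power runs from 1.7% to 68%. It is below 30% in six of eight scenarios.
- If 70% to 80% of the 50-week hazard fell before Week 26, pooled detection for 20% versus 5% would be 41% to 46%, not 61%. That front-loading is an assumption. It is plausible because the corticosteroid taper in Protocol Table 10 ends at Week 12.

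**The case against.** The main objection is that nothing is lost. Weeks 26 to 50 are tabulated by randomized arm, and SAP 5.6 puts all safety data in patient listings. No safety test or power is planned either. This is correct. A reader might infer that LN safety data stop at Week 26, or that much of a planned power is forfeited. The documents support neither reading.

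A reader might also say that the arms are never compared over 50 weeks, or that the Extension table covers only those who reached Week 26. The first cannot be established: SAP 1 puts table specifications in a separate Data Presentation Plan, which is not among these documents. The second is not in the text: SAP 5.6.2 uses treated Safety Set participants as the denominator and gives no separate one for the Extension Period.

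Week 26 is also not an empty landmark in LN. Additional standard-of-care therapy for Suboptimal Response becomes allowed (Protocol 3.2.3 and 6.6), steroid tapering below the target becomes discretionary (Protocol 6.5.1), and the sponsor is unblinded for the primary analysis. This is a good reason to keep the period tables. It does not argue against adding a cumulative one.

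Finally, Table 6 attributes the increased infection risk in LN to the immunosuppressants, which both arms receive, and says the relevance of serious infection for ravulizumab is unconfirmed. The passage motivates looking at infections over the full period. It does not show that an excess is expected.

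**Conclusion.** The point holds as a gap in the specified displays. For LN, neither document specifies a Day 1 to Week 50 participant-level AE, SAE or AESI summary by arm, and the specified tables cannot be combined to produce one. No planned inference is wrong and no data are discarded.

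The size is modest. Against both period tables read together, the pooled table adds about 5 to 9 points of detection in the scenarios tried. That rests on assumed event rates, constant hazard and a test the plan does not include. With 40 versus 20 participants, detection is weak for small or rare differences whichever display is used. The stronger reason for the change is descriptive: cumulative incidence by arm is the direct summary of the safety endpoint over the randomized period, and it is almost free. The point does not extend to IgAN, where the Week 26 split is appropriate.

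**What to change.** In SAP 5.1 and 5.6, and in Protocol 9.4 at the next amendment, add for the LN cohort a cumulative set of safety tables: TEAE, TESAE, SOC/PT, severity, relationship and AESI. They should run from the first dose to 56 days after the last dose, by treatment arm in the Safety Set, with each participant counted once per category.

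Keep the by-period tables for both cohorts. Add a note that additional standard-of-care therapy, including that allowed for Suboptimal Response after Week 26, affects how the cumulative tables are read.

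The cost is a wording change and one extra run of existing tables for one cohort. No new data are needed.
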